#### 5.1.1. ODI

Improvement in the Oswestry Disability Index (ODI) is the primary clinical status indicator among non-Treatment Failures. ODI has become one of the principal condition-specific outcome measures used in the management of spinal disorders. The ODI is a self-rating patient questionnaire that is comprised of ten items that reflect patients’ ability to manage their everyday life while dealing with their pain. Every selectable answer is linked to an amount of points from 0 to 5. A maximum of 50 points can be reached. The primary variable will be expressed as a percentage of the maximum possible value. The following are interpretations of these percentages: 0% to 20% - minimal disability; 21% to 40%, moderate disability; 41%-60% severe

 Fairbank J.C.T., The Oswestry Disability Index, Spine Volume 25, Number 22, pp 2940–2953, 2000

disability; 61%-80% - crippled; 80% to 100%, bed-bound or exaggerating symptoms. An increase from baseline of 15 is required for primary composite clinical success.

### **5.1.2. Secondary Surgical Interventions**

Reoperations, revisions, removals and supplemental fixation are defined as follows:

- A revision is a procedure that adjusts or in any way modifies or removes part of the original implant configuration, with or without replacement of a component. A revision may also include adjusting the position of the original configuration.
- A removal is a procedure where all of the original system configurations are removed with or without replacement.
- A reoperation is any surgical procedure at the involved level(s) that does not remove, modify, or add any components to the system. Note: a surgery to alleviate post-operative superficial wound problems within the immediate post-operative 30 day window will not be considered a treatment failure.
- A supplemental fixation is a spinal procedure in which additional instrumentation not under study in the protocol is implanted (e.g., supplemental placement of a rod/screw system or a plate/screw system) at the index level(s).

If a subject in either study group undergoes a reoperation, revision, removal, or supplemental fixation procedure, the subject should remain in the study and should continue to be followed up within the study. Such patients will be considered a Treatment Failure.

### **5.1.3. Lumbar Injections**

All lumbar injections will be captured as part of the study. A lumbar injection is defined as any deep injection into the spine, typically under image-guidance, of steroids and/or other pharmacologic agents (e.g. facet injections or epidural injections by the transforaminal, interlaminar, or caudal routes). Other types of injections such as trigger point injections, intramuscular injection for systemic administration of steroids, dry-needling, prolotherapy, or acupuncture, will be captured but will not be considered study failures.

Any patient receiving a lumbar injection including epidural injection, nerve root blocks and facet blocks on or before the Month 24 is considered a Treatment Failure and so will not have achieved Month 24 composite clinical success. Patients receiving a lumbar injection within 12 months of their Month 60 interval will be failures for Month 60 CCS since their clinical data is no longer evaluable due to the potential confound of a successful secondary treatment for a failed index treatment. Similarly, when determining intermediate CCS at Month 36 and Month 48, lumbar epidural injections within 12 months of these clinic visits will indicate CCS failure for that time point, but not necessarily for subsequent time points. Additionally, patients receiving 2 or more series of injections as defined above will be CCS failures for all later time points. A separate sensitivity analysis will also be performed within Objective 4 where all patients who receive lumbar injections at any time prior to Month 60 will be counted as Treatment Failures.

## **5.2. Secondary Variables of Performance**

Secondary evaluation criteria include:

- ODI change compared to baseline at 24 and 60 months as a continuous variables and in terms of achieving at least a 15 point improvement.
- Change in Visual Analog Scale (VAS) for low back pain (on the 100 mm scale) after 24 and 60 months compared to baseline as a continuous variables and in terms of achieving a 20 point improvement.

- Change in leg pain using a Visual Analog Scale (VAS) 100 mm scale after 24 and 60 months compared to baseline as a continuous variable and in terms of achieving a 20 point improvement.
- Change of Zurich Claudication Questionnaire (ZCQ) after 24 and 60 months compared to baseline:
  - Symptom severity (range 1-5)
  - Physical function (range 1-4)
  - Patient satisfaction (range 1-4, no baseline)
  - ZCQ Overall Success ( $\geq 2$  of 3 of the following)
    1. Improvement in symptom severity  $\geq 0.5$
    2. Improvement in physical function  $\geq 0.5$
    3. Satisfied or somewhat satisfied as defined by a score of  $\leq 2.5$  points on the patient satisfaction domain.
  - ZCQ Overall Success components.
- Maintenance or improvement in EQ-5D compared to baseline.
- Change from baseline to Month 24 and Month 60 in maximum walking time from treadmill test as a continuous variable and in terms of achieving at least an 8 minute improvement or maximum time of 15 minutes.
- Change from baseline to Month 24 and Month 60 in time to symptoms from treadmill test as a continuous variable and in terms of achieving at least an 8 minute improvement or maximum time of 15 minutes
- Neurological status (assessment of maintenance of improvement after surgery throughout study duration)
- Radiography Endpoints
  - Assessment of significant migration of the implant or the complete expulsion (significant is defined  $> 5$  mm).
  - Assessment of spinous process fracture.
  - Assessment of maintenance of foraminal height
  - Assessment of adjacent level disease determined by independent radiographic review
- Correlation of foraminal height changes to improvement of walking distance on a treadmill (after 24 and 60 months compared to baseline). No persistent new or worsening sensory or motor deficit where persistence is established by identifying new or worsening deficits at Month 12 that do not resolve by Month 24. For Month 60 CCS, this will be established by identifying new or worsening deficits at Month 48 that do not resolve by Month 60.
- Presence of a major device-related adverse event defined as an event simultaneously both 'Serious' and 'Definitely' related to the implant on or before the exact surgical two-year anniversary or exact five-year anniversary.
- The CCS will be modified to examine the effect narcotics use (opioids and/or opiates) has on treatment success rates. When comparing coflex in conjunction with decompression to decompression alone, this modified Month 24 CCS will include:
  - No "Treatment Failure" on or before the exact 2-year anniversary of the index surgery. Treatment Failure will include:
    - No surgical intervention at the index level
    - No lumbar epidural steroid injection including nerve root blocks and facet blocks at any lumbar level
    - No persistent new or worsening sensory or motor deficit where persistence is established by identifying new or worsening deficits at Month 12 that do not resolve by Month 24.
    - No major device-related adverse event defined as an event simultaneously both 'Serious' and 'Definitely' according to independent Clinical Events Committee (CEC) related to the implant on or before the exact surgical two-year anniversary or exact

five-year anniversary. In the decompression alone group, since there is no device, this endpoint will be identified as any serious AE that is classified as definitely related to surgery.

- No use of a narcotic (opioids or opiates) at Month 24.

### **5.2.1. Walking Distance Test on a Treadmill**

Patients will perform a walking distance test on a treadmill at screening (visit 1) and post-operatively. It will be assessed if a patient can walk on the 0° ramp incline at a speed of 1.2 miles/hour for 15 minutes (according to the publication by Deen).

Also assessed will be time to first symptoms, time to severe symptoms and nature of symptoms (leg weakness, leg pain, back pain, or generalized fatigue, other). A time of zero will be recorded when symptoms were present at onset. The examination will be stopped after 15 minutes or at the onset of severe symptoms.

**Definition of severe symptoms is:** The level of discomfort that would make patients stop their activities in usual life situations. Patients will be instructed to walk with an upright posture. They are not permitted to lean forward or to hold onto the handrails during examination.

It is assumed that patients with additional back pain will have more problems in managing the complete walking distance and therefore may stop the walking distance test before the endpoint at 15 min.

The investigator has to check whether the patient shows any medical contraindication against the performance of a walking distance test (Deen 1995, p 28).

If the patient is not able to perform the walking distance test at any of the clinical visits it does not lead to an exclusion of the study.

In summary, the primary endpoints from the treadmill test will be:

- Change from baseline to Month 24 and Month 60 in maximum walking time from treadmill test as a continuous variable and in terms of achieving at least an 8 minute improvement or maximum time of 15 minutes.
- Change from baseline to Month 24 and Month 60 in time to symptoms from treadmill test as a continuous variable and in terms of achieving at least an 8 minute improvement or maximum time of 15 minutes.

### **5.2.2. VAS**

Change in Visual Analog Scale (VAS) for low back pain (on the 100 mm scale) after 24 and 60 months compared to baseline as a continuous variables and in terms of achieving a 20 point improvement.

Change in right leg pain and left leg pain using a Visual Analog Scale (VAS) 100 mm scale after 24 and 60 months compared to baseline as a continuous variable and in terms of achieving a 20 point improvement.

### **5.2.3. Zurich Claudication Questionnaire (ZCQ)**

Change of Zurich Claudication Questionnaire (ZCQ) after 24 and 60 months compared to baseline:

- Symptom severity (range 1-5)
- Physical function (range 1-4)
- Patient satisfaction (range 1-4, no baseline)
- ZCQ Overall Success ( $\geq 2$  of 3 of the following)
  - Improvement in symptom severity  $\geq 0.5$
  - Improvement in physical function  $\geq 0.5$
  - Satisfied or somewhat satisfied as defined by a score of  $\leq 2.5$  points on the patient satisfaction domain.
- ZCQ Overall Success components

#### **5.2.4. EQ-5D**

Maintenance or improvement in EQ-5D (quality of life) after 24 and 60 months compared to baseline.

#### **5.2.5. Neurological Changes**

No persistent new or worsening sensory or motor deficit where persistence is established by identifying new or worsening deficits at Month 18 that do not resolve by Month 24 for assessment of Month 24 CCS. Each individual assessment is evaluated separately by side (right or left) and by anatomic location as appropriate. Any specific sub test that indicates a deficit at Month 18 that was not present at baseline or for which there is a worsening at Month 18 relative to baseline that does not return to baseline or better status by Month 24 will be identified. Specific sub tests will be aggregated into summary endpoints (e.g., muscle strength deficit and sensory deficit) as well as into an overall summary variable that is included in the overall composite clinical success endpoint.

A similar definition will be used for Month 60 CCS. No persistent new or worsening sensory or motor deficit where persistence will be established by identifying new or worsening deficits at Month 48 that do not resolve by Month 60 for assessment of Month 60 CCS.

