	
 
• Change from baseline to Month 24 and Month 60 in maximum walking time from treadmill test as a continuous variable and in terms of achieving at least an 8 minute improvement or maximum time of 15 minutes.
 
• Change from baseline to Month 24 and Month 60 in time to symptoms from treadmill test as a continuous variable and in terms of achieving at least an 8 minute improvement or maximum time of 15 minutes.
 
• Neurological status (motor, sensory, reflex, SLR - assessment of maintenance of improvement after surgery throughout study duration).
 
• Radiography Endpoints 
 
1. Assessment of significant migration of the implant or the complete expulsion (significant is defined > 5 mm).
 
2. Assessment of spinous process fracture.
 
3. Assessment of maintenance of foraminal height
 
4. Assessment of adjacent level disease determined by independent radiographic review
 
 
 
• Correlation of foraminal height changes to improvement of walking distance on a treadmill (after 24 and 60 months compared to baseline).
 
• The CCS will be modified to examine the effect narcotics use (opioids and/or opiates) has on treatment success rates. When comparing coflex® in conjunction with decompression to decompression alone, this modified Month 24 CCS will include: 
 
• No “Treatment Failure” on or before the exact 2-year anniversary of the index surgery. Treatment Failure will include: 
 
1. No surgical intervention at the index level
 
2. No lumbar epidural steroid injection including nerve root blocks and facet blocks at any lumbar level
 
 
 
• No persistent new or worsening sensory or motor deficit where persistence is established by identifying new or worsening deficits at Month 18 that do not resolve by Month 24.
 
• No major device-related adverse event defined as an event simultaneously both ‘Serious’ and ‘Definitely’ according to independent Clinical Events Committee (CEC) related to the implant on or before the exact surgical two-year anniversary or exact five-year anniversary. In the decompression alone group, since there is no device, this endpoint will be identified as any serious AE that is classified as definitely related to surgery.
 
 
 

--	--

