### **3.2. Primary Endpoints**

The identical Month 24 CCS endpoint as was used in the IDE will be used to compare PAS results to IDE study results, and to update the Bayesian posterior probabilities of non-inferiority and superiority relative to fusion. This CCS definition requires no Treatment Failure (i.e., no reoperation, revision, replacement, or supplemental fixation at the index level(s) and no epidural injection at any lumbar level); an ODI improvement  $\geq 15$ ; as well as no new or worsening, persistent neurological deficit; and no major device-related adverse event defined as severe and definitely-related

The CCS endpoints using in Objective 2 and 3 replace severe device-related AEs with serious device-related AEs for greater consistency with other spine studies. The relationship will be evaluated relative to the device and the surgical procedure since controls receive no device. For comparison to decompression alone, any surgical intervention at the index site will imply clinical failure.

Month 60 success for this comparison will require the following items:

- At least a 15 point improvement relative to pretreatment baseline in the Oswestry Disability Index (ODI, range 0-100).
- No reoperations, revisions, removals, or supplemental fixation at the index level(s);
- No  $\geq 2$  injections or series of injections for any lumbar level\*\*, or nerve block procedures performed to treat spinal stenosis at any lumbar level(s); or a single injection within 12 months of the 5 year endpoint.

\*\*A series of injections is considered 2-3 injections performed between 24-hour and one week intervals designed to treat a single pain event. Secondary injections performed due to patient demand or recurrence of symptoms following the initial injection are considered separate injections and would constitute a study failure.

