#### **4.8.4. *Visit 4: 12 months follow up (±2 month)***

- VAS leg pain
- VAS back pain
- Questionnaires ODI, ZCQ, EQ-5D, patient satisfaction, status of employment / pension
- Physical examination
- Neurological status
- Pain management
- Hospitalization
- Follow up treatment
- X-ray images for both groups in all four positions
- Walking distance test

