#### **4.8.5. *Visit 5: 24 months follow up (±2 month)***

- VAS leg pain
- VAS back pain
- Questionnaires ODI, ZCQ, EQ-5D, patient satisfaction, status of employment / pension
- Physical examination
- Neurological status
- Pain management
- Hospitalization

- Follow up treatment
- X-ray images for both groups in all four positions
- CT Scan for all subjects
- Walking distance test

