#### **4.8.10. Schedule of Study Visits**

A tabular summary of visit schedule is provided below.

Visits	Screening		Follow-Up						Final Report
	1 < 4 weeks before d0	2 day 0 surgery	3 months after surgery (±2 weeks)	4 12 months after surgery (±2 month)	5 24 months after surgery (±2 month)	6 36 months after surgery (±4 months)	7 48 months after surgery (±4 months)	8 60 months after surgery (±4 months)	
Patient information and Informed consent	X								
Demographics	X								
Medical history	X								
Pain management	X	X 	X	X	X	X	X	X	
Physical examination	X 		X 	X 	X 	X 	X 	X 	
Neurological status	X	X 	X	X	X	X	X	X	
Inclusion/exclusion criteria	X	(X)							
X-ray in standing position (AP, lateral, flexion, extension)	X	X 	X	X	X 	X	X	X 	
MRI and/or Post Myelo CT (not older than 6 months)	X								
Diagnosis	X								
Walking Distance Test (treadmill)	X		X	X	X	X	X	X	
VAS back pain, VAS leg pain	X		X	X	X			X	
ODI, ZCQ, EQ-5D	X		X	X	X	X	X	X	
Surgery		X							
Patient's satisfaction questionnaire			X	X	X	X	X	X	
Documentation of AEs		X	X	X	X	X	X	X	

1) A detailed physical examination will be performed at visit 1. In the following visits only a routine physical examination will be performed and changes compared to screening will be recorded. The investigator is free to perform a complete physical examination.

2) Only group B (with coflex® implant: anterior-posterior, lateral).

3) After surgery, before discharge.

4) CT Scans will be conducted at 24 months for all subjects and at 60 months for all symptomatic, confirmed spinous process fracture subjects.

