## 5. Performance Evaluation and Measurements

### 5.1. Primary Variables of Performance

Month 60 composite success will require the following items (Objective 1):

- At least a 15 point improvement relative to pretreatment baseline in the Oswestry Disability Index (ODI, range 0-100).
- No reoperations, revisions, removals, or supplemental fixation at the index level(s);
- No  $\geq 2$  injections or series of injections for any lumbar level\*\*, or nerve block procedures performed to treat spinal stenosis at any lumbar level(s); or a single injection within 12 months of the 5 year endpoint.

\*\*A series of injections is considered 2-3 injections performed between 24-hour and one week intervals designed to treat a single pain event. Secondary injections performed due to patient demand or recurrence of symptoms following the initial injection are considered separate injections and would constitute a study failure.

For Objectives 2 and 3, the Month 24 CCS from the IDE will be slightly modified to include any surgical intervention at index level(s). This is because the decompression only group receives no device. In summary, when comparing coflex® in conjunction with decompression to decompression alone, Month 24 CCS will require.

- No “Treatment Failure” on or before the exact 2-year anniversary of the index surgery).
- At least a 15 point improvement relative to pretreatment baseline in the Oswestry Disability Index (ODI, range 0-100).
- No persistent new or worsening sensory or motor deficit where persistence is established by identifying new or worsening deficits at Month 12 that do not resolve by Month 24.
- No major device-related adverse event defined as an event simultaneously both ‘Serious’ and ‘Definitely’ related to the implant on or before the exact surgical two-year anniversary.

Treatment Failure will include:

- No surgical intervention at the index level
- No lumbar epidural steroid injection including nerve root blocks and facet blocks at any lumbar level.

The identical Month 24 CCS endpoint used in the IDE study will be used to compare PAS results to IDE study results and to update the Bayesian posterior probabilities of non-inferiority and superiority relative to fusion (Objective 4).

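### The neurological item of the Month 24 composite has two conflicting rules, one resting on a Month 18 assessment that is not scheduled, and its visit pair for Objective 4 is not stated

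*Combined protocol and SAP*

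**What the plan says.** **Month 18.** Section 5.2.5 sets out how the neurological item is scored: each sub-test separately, by side and location, then aggregated. The starting point is "Any specific sub test that indicates a deficit at Month 18 that was not present at baseline", or a worsening at that time, which has not returned to baseline status by Month 24. The result feeds an "overall summary variable that is included in the overall composite clinical success endpoint". The synopsis, in its narcotics-modified Month 24 composite, also relies on "identifying new or worsening deficits at Month 18 that do not resolve by Month 24".

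**Month 12.** Section 5.1, which lists the primary variables, defines the item for Objectives 2 and 3 by "identifying new or worsening deficits at Month 12 that do not resolve by Month 24". Sections 3.3 and 5.2 also use Month 12.

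**Schedule.** Sections 4.8.1 to 4.8.8 and the table in 4.8.10 place neurological status at screening, before discharge, and at Months 3, 12, 24, 36, 48 and 60.

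**Objective 4.** Section 3.2 states: "The identical Month 24 CCS endpoint as was used in the IDE will be used to compare PAS results to IDE study results". It includes absence of a persistent neurological deficit among the requirements, without naming the visits that establish persistence.

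**Objectives 2 and 3.** The definitions in the synopsis and in section 3.1 contain no neurological item. Section 5.1 does.

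**The concern.** A component of a primary composite has two incompatible definitions. The more detailed one, which a programmer would naturally turn to, asks for an examination that nobody is scheduled to have. The plan does not say whether a patient without a Month 18 examination passes the item or is missing on it. If the choice between the rules is left until the outcomes are known, it can be made with knowledge of its effect.

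Objective 4 is the most exposed. The PAS success rate is set against a count already fixed, 135 of 204. If the item works in the IDE count but cannot fail anyone in the PAS, the PAS rate can only move upward, towards non-inferiority. Even if the item works in both studies, two different visit pairs would make the endpoints differ.

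**Working it through.** **1. Can the 5.2.5 rule be carried out?** The Month 12 and Month 24 visits each have a window of ±2 months. The latest Month 12 visit falls at 12 + 2 = 14 months and the earliest Month 24 visit at 24 − 2 = 22 months, so neither window reaches Month 18. Section 4.8.9 lists pain scales, questionnaires and the walking test for unscheduled visits, but no neurological examination. No planned assessment supplies a Month 18 finding. Read literally, 5.2.5 identifies no persistent deficit from scheduled data.

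**2. Can the Month 12 rule be carried out?** Yes. Neurological status is listed at both Month 12 (4.8.4) and Month 24 (4.8.5). A deficit that first appears after the Month 12 visit is not counted under this rule.

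**3. Reproducing the plan's Objective 4 figures.** Inputs from section 7.7.4: IDE count 135/204, margin 0.1175, posterior threshold 0.95, non-informative priors. Section 4.2 gives N = 150. Assumption: the non-informative prior is the Jeffreys beta(0.5, 0.5); beta(1, 1) gives the same cut-off.

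- IDE rate: beta(135.5, 69.5).
- PAS rate after x successes: beta(x + 0.5, 150 − x + 0.5).
- Conclude non-inferiority if P(PAS rate > IDE rate − 0.1175) ≥ 0.95.
- The smallest qualifying x is 95, so at least 95/150 = 63.3% is needed.
- Power = P(X ≥ 95) with X ~ Binomial(150, 0.662) = 0.797. The plan states about 80%.
- Type 1 error as the plan evaluates it, at 0.662 − 0.10 = 0.562: P(X ≥ 95) = 0.046. The plan states 0.045, from simulation.

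The plan's figures reproduce, and they do not depend on the Month 12 or Month 18 wording.

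**4. What if the item failed nobody in the PAS?** Let q be the share of patients who fail on the neurological item alone. The scored rate is then the true rate plus q, while the cut-off stays at 95. The documents do not give q, so 1 to 3 points are assumed. Two true rates are shown: 0.562, where the plan evaluates type 1 error, and 0.662 − 0.1175 = 0.5445, the boundary of the 0.1175 margin.

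| Assumed q | Chance of concluding non-inferiority at 0.562 | At 0.5445 |
|---|---|---|
| 0 | 4.6% | 1.7% |
| 1 point | 7.5% | 3.1% |
| 2 points | 11.6% | 5.2% |
| 3 points | 17.2% | 8.4% |

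Both rates are shown because section 7.6 writes the Objective 4 hypotheses with a margin of 0.10, whereas the synopsis and 7.7.4 use 0.1175. Under the 0.1175 margin, 0.562 is not the null boundary.

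**5. If the item is read at Months 12 and 24,** patients can fail it, step 4 does not apply, and the figures in step 3 stand.

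**The case against.** The strongest reply is that the plan already contains a workable rule. Section 5.1 is the primary-variable section and uses Month 12, in agreement with 3.3 and 5.2. Month 18 appears only in 5.2.5, which sits under secondary variables, and in a secondary endpoint of the synopsis. This stands, and it rules out one tempting inference, that no patient can fail the neurological item. That follows only if 5.2.5 is taken alone and an absent examination counts as a pass; it could as well count as missing.

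A reader might also infer that the PAS rate is not comparable with the IDE rate. The documents do not support that either. They never state the IDE visit pair, so a mismatch cannot be demonstrated. The summary of IDE success criteria in section 2 does not even list a neurological item, although 3.2 does.

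The sizes in the table are also open to challenge. They need a wholly inert item and an assumed q, and at the 0.1175 boundary a 1-point shift leaves the error rate below 5%. This too stands.

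What the reply does not remove is that 5.2.5 explicitly feeds the composite, is the only place with scoring detail, and cannot be executed. Nor does it supply the visit pair that a claim of identity with the IDE endpoint requires.

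**Conclusion.** The point holds as a contradiction that affects a primary composite, and it is more than clerical. Section 5.2.5 and the synopsis establish persistence from an unscheduled Month 18 assessment; 3.3, 5.1 and 5.2 use the scheduled Month 12. For Objective 4, comparability with 135/204 is unresolved.

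Any numerical effect is conditional. It arises only if the item is scored so that nobody can fail it, and its size depends on q. If that happened, the direction would be towards non-inferiority, with the error rate passing 5% at an assumed 1 point when judged at 0.562, or at 2 points when judged at 0.5445. These figures illustrate sensitivity and do not estimate bias in this trial.

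**What to change.** 1. In section 5.2.5 and in the synopsis, replace Month 18 with the scheduled Month 12 to Month 24 pair already used in 3.3, 5.1 and 5.2.
2. Decide whether the neurological item belongs in the Objectives 2 and 3 composite, and make the synopsis, 3.1 and 5.1 agree.
3. Before Month 24 outcomes are unblinded, state the IDE visit pair for Objective 4. If it is not Months 12 and 24, either re-score the IDE patients with that pair or report Objective 4 with the item removed from both studies. In either case, stop calling the endpoint identical.

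A sensitivity analysis that uses the Month 36 visit to confirm deficits first seen at Month 24 is optional; it would have to wait for Month 36 data.

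**Cost.** Steps 1 and 2 are changes of wording, and no visit is added. Both routes in step 3 need item-level IDE data; section 7.1 says that patient-level IDE data are used to form the priors. A re-scored count may move slightly from 135/204. That count also underlies the beta(135.5, 69.5) prior for Objectives 2 and 3 and the IDE posterior probabilities to be updated under Objective 4, so the plan should say whether those change with it.
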